1.0 Study Summary

Study Title	Ultrasound to verify lung-isolation during single-lung ventilation
Study Design	Prospective study
Primary Objective	To determine the accuracy of auscultation and ultrasonography for confirming lung isolation during SLV, as compared to direct visualization using FOB (gold standard).
Secondary Objective(s)	To compare the time required to confirm lung isolation using the above-mentioned techniques including auscultation, FOB, and ultrasound.
Research Intervention(s)/ Investigational Agent(s)	Ultrasound and auscultation of the chest.
IND/IDE #	N/A
Study Population	Main OR surgical patients
Sample Size	80
Study Duration for individual participants	Less than 30 minutes total.
Study Specific Abbreviations/ Definitions	FOB – Fiberoptic bronchoscope SLV – Single-lung ventilation DLT – Double-lumen endotracheal tube ETT – Endotracheal tube

2.0 Objectives

- 2.1 The primary objective is to determine the accuracy of auscultation and ultrasonography for confirming lung isolation during SLV, as compared to direct visualization using FOB (gold standard). The secondary objective is to compare the time required to confirm lung isolation using the above-mentioned techniques including auscultation, FOB, and ultrasound.
- 2.2 The hypothesis is that ultrasonography will have at least 80% accuracy for verifying lung separation during SLV as confirmed by FOB; and will have greater accuracy than auscultation.

3.0 Background

- 3.1 During thoracic surgery, specific anesthetic techniques are used to isolate the lungs and allow for single-lung ventilation (SLV) so that the ipsilateral lung is not ventilated during the surgical procedure.¹⁻³ A motionless lung on the side of surgery is necessary to allow for the surgical procedure to proceed optimally. To accomplish SLV, there are several options including use of a specialized double-lumen

PROTOCOL TITLE: Ultrasound to verify lung-isolation during single-lung ventilation

endotracheal tube (DLT), placement of a bronchial blocker into the main stem bronchus of the operative side, or selective main stem intubation with a standard endotracheal tube (ETT). All of these devices allow for selective ventilation of the non-operative lung. In common clinical practice, the placement of the device for SLV may be guided by direct vision using a fiberoptic bronchoscope (FOB) and/or differential auscultation of the two lungs.

More recently, there has been increased use of ultrasonography at the bedside in various clinical locations including the Pediatric ICU and the operating room. Ultrasonography is painless, non-invasive and carries no risk. Given its ease of use and non-invasive nature, ultrasound is being used more frequently to make thoracic diagnoses including hemothorax, pneumothorax, pneumonia, and ARDS.³⁻⁸ More recently, preliminary data from three studies in adults suggest that ultrasound can be used to confirm lung isolation during SLV.⁹⁻¹¹ When the lung is not ventilated, there is no pleural movement noted (absence of lung sliding and no B-lines) and as the lung is non-mobile, the cardiac impulses may be transmitted through the lung to the chest wall and can be seen (presence of lung pulse). To date, there is only one anecdotal report of the intraoperative use of thoracic ultrasonography in the pediatric-aged patient.¹² The purpose of the current study is to prospectively evaluate the usefulness of thoracic ultrasonography in demonstrating effective lung isolation during SLV in the pediatric patient. Our primary hypothesis is that ultrasound will accurately verify lung separation during SLV, as compared to FOB.

- 3.2 This would provide a rapid and non-invasive means to demonstrate effective lung isolation without the time, cost, and invasive nature of direct visualization using a FOB.

4.0 Study Endpoints

- 4.1 The accuracy of using ultrasound to assess lung isolation by visualizing lung movement or lack thereof of both the operative and non-operative lung fields.
- 4.2 Time to confirm lung isolation.

5.0 Study Intervention/Investigational Agent

- 5.1 The only intervention being used that is not normally used in general clinical practice is the use of ultrasonography. The technique is non-invasive and poses no risk. Ultrasonography will be performed by an anesthesiologist with training and experience and will add less than 10 minutes to the anesthetic time.

6.0 Procedures Involved*

PROTOCOL TITLE: Ultrasound to verify lung-isolation during single-lung ventilation

6.1 The proposed study will be conducted in 80 patients, ranging in age from 0 to 21 years. There will be no change in clinical practice regarding choice of anesthetic technique including premedication, device used for SLV, monitoring, induction, and maintenance of anesthesia. An investigator will identify patients in whom SLV is required for thoracic surgery. There will be total of three anesthesia providers and one surgeon involved in the study. One will be the primary anesthesiologist, who is one of the attending faculty and will be responsible for patient care during the perioperative period. They will decide prior to and during the case whether the patient is appropriate for and able to complete the study protocol. The other two anesthesia providers will be members of the study team or other anesthesia attending/fellow and will include an auscultator (may be a resident/CRNA/SRNA), the anesthesia provider who will perform the auscultation examination and the ultrasonographer, the anesthesia provider who will perform the ultrasound examination (see below). The surgeon will be the attending surgeon and will confirm the efficacy of one-lung ventilation during the surgical procedure. Both the auscultator and ultrasonographer will be blinded to the lung that is isolated.

The technique of SLV will be determined by the attending anesthesiology to include a DLT, bronchial blocker or main stem intubation with an ETT. The ventilator settings will be standardized until all of the study measurements and data have been collected:

Ventilation Mode: PRVC

RR titrated to achieve normocapnia

Inspiratory time 1 second

TV set at 6-8 ml/kg

PEEP: minimum of 5 cm H20

100% FiO2

6.2 After anesthetic induction the following ventilatory parameters will be recorded: tidal volume, peak inflating pressure, inspiratory time, respiratory rate, inspired oxygen concentration, end-tidal carbon dioxide, and oxygen saturation. After placement of the device for SLV, and isolation of the lung, the non-operative lung will be ventilated and the ventilatory parameters will be recorded again. Clinical confirmation of effective lung separation will include auscultation with documentation of absence of breath sounds on the operative side. Following this, correct placement of the DLT will be confirmed using FOB. The time to perform FOB will be determined.

6.3 Once SLV device placement is confirmed by bronchoscopy, the patient's face and airway management devices will be covered by a drape to blind to auscultator and ultrasonographer. The auscultator

PROTOCOL TITLE: Ultrasound to verify lung-isolation during single-lung ventilation

and ultrasonographer will then enter the room. The auscultator will evaluate lung isolation and note the results. The ultrasonographer will then evaluate lung isolation with absence of lung sliding and the presence of lung pulse on the operative (non-ventilated) lung, and B-line. The procedure time for each (auscultation and ultrasonography) will be determined. Procedure time will be calculated from the time that the participant touches the patient to the completion of the examination (auscultation or ultrasonography). After the completion of the ultrasound examination, the patient will be placed in the surgical position. Following this, the surgical procedure will be started and lung separation documented by the surgeon. If lung separation was not successful, this will be noted. The intraoperative ventilation strategy will be at the discretion of the attending anesthesiologist.

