17.0 Data Management* and Confidentiality

17.1 We will compare the accuracy, sensitivity, and specificity of ultrasonography and auscultation (using FOB confirmation of one-lung isolation as the reference standard) using paired tests of proportions. As a secondary, exploratory aim, we will compare the time to perform each of the techniques using paired t-tests or sign-rank tests (according to the normality of the outcome distribution).

17.2 Research records will be stored in a locked cabinet and password protected computer. Only certified research personnel will be given access to identifiable subject information

17.3 Following publication of study results, research records will be stored for a period of 3-5 years and then will be destroyed by placing in a secure shredding bin.

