25.0 Resources Available

25.1 The department of Anesthesiology and Pain Medicine has 2 research coordinators and 2 research associates that will be enrolling subjects for this study. All study staff will be trained on the study procedures.

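### Examiners are blinded only to which lung is isolated and their recorded answer is undefined, so the accuracy figure can show identification of the isolated side but not verification of isolation

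*Combined protocol and SAP*

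**What the plan says.** All references are to the combined protocol and SAP.

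- **Blinding (6.1).** "Both the auscultator and ultrasonographer will be blinded to the lung that is isolated". Nothing is said about concealing whether a lung is isolated.
- **Sequence (6.3).** The examinations start only "Once SLV device placement is confirmed by bronchoscopy" and the face and airway devices have been draped. The auscultator "and ultrasonographer will then enter the room". No two-lung, sham or unconfirmed-placement condition is described.
- **Training (25.1).** "All study staff will be trained on the study procedures".
- **Recorded answer (4.1, 6.3).** The endpoint rests on "visualizing lung movement or lack thereof of both the operative and non-operative lung fields". Section 6.3 says that results are noted, but lists no response categories and gives no rule for an indeterminate examination.
- **Claim (2.2, 3.2).** The hypothesis is that "ultrasonography will have at least 80% accuracy for verifying lung separation during SLV as confirmed by FOB", and that ultrasound is more accurate than auscultation. Section 3.2 presents ultrasound as a way to demonstrate effective isolation without bronchoscopy.
- **Analysis (17.1).** "We will compare the accuracy, sensitivity, and specificity of ultrasonography and auscultation", with bronchoscopy as the reference standard and paired tests.

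**The concern.** An accuracy figure has meaning only relative to the question the examiner was answering and what the examiner already knew. An examiner who knows that one lung has just been isolated under bronchoscopic control is not being asked whether isolation has been achieved. At most, the open question is which side.

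That is an easier task than the one named in 2.2, and it has a guessing level that the plan does not mention. The 80% benchmark could be met, and the result read as evidence that ultrasound can stand in for bronchoscopy, although no examiner had to decide whether isolation was present. The comparison with auscultation is also affected, because guesses on both sides pull the two accuracies together. Since the response format is undefined, readers of the eventual result could not tell how much of the figure is detection.

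**Working it through.** **1. The plan's own figure.** Section 12.2 gives an accuracy of 85%, a difference of 10 points, 80 patients, a two-tailed one-sample test of proportions and power above 80%. Alpha is not stated; 0.05 two-sided is assumed.

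Power = Φ[(|p1 − p0|√n − 1.96√(p0(1 − p0))) / √(p1(1 − p1))].

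- p0 = 0.85, p1 = 0.95, n = 80: (0.894 − 0.700)/0.218 = 0.89, so power is 81.4%. The stated figure reproduces when 85% is the null value.
- p0 = 0.75, p1 = 0.85: power is 55.1%.

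This calculation treats accuracy as a plain proportion. It makes no reference to a guessing level, and the present point does not change N = 80.

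**2. What the examiners can know.** Placing 6.1, 6.3 and 25.1 side by side: only the side is concealed, entry follows bronchoscopic confirmation, and study staff are trained on the procedures. It follows, by inference, that an examiner can know one lung is isolated.

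**3. Reading A: the recorded answer is left or right.** Assume an examiner truly detects the side in a fraction d of patients and otherwise guesses with probability 1/2 of being right.

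Accuracy = d + (1 − d)/2, so d = 2 × accuracy − 1.

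| Observed accuracy | Detection d |
|---|---|
| 75% | 50% |
| 80% (benchmark in 2.2) | 60% |
| 85% (planning value in 12.2) | 70% |

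For two techniques U and A, accuracy(U) − accuracy(A) = (d(U) − d(A))/2. The observed difference is half the detection difference, whatever the rates. For example, detection of 70% against 50% (20 points) appears as 85% against 75% (10 points).

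Could guessing alone pass? With 80 patients and a 50% chance each, the probability of 64 or more correct (64/80 = 80%) is 2.9 × 10⁻⁸. It could not.

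**4. Reading B: the recorded answer is isolated yes or no.** If every examined patient is confirmed by bronchoscopy, as the sequence in 6.3 implies, always answering yes is correct in 80 of 80, or 100%. If an assumed fraction f of examined patients were not isolated, the same empty strategy would score 1 − f: 95% at f = 5% and 90% at f = 10%. Both exceed the 80% benchmark.

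**5. Comparison with the claim.** Reading A measures side identification above a 50% floor. Reading B can be satisfied with no examination at all. Neither yields the quantity in 2.2, "at least 80% accuracy for verifying lung separation during SLV as confirmed by FOB".

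**The case against.** The strongest reply is that both steps are inference. No sentence says the examiners know a lung is isolated, and none imposes a forced left/right call. The endpoint in 4.1 looks at both lung fields, which leaves room for both moving or for an equivocal finding. This stands, and it is why the point is put as two readings. It does not rescue 2.2, because the alternative yes/no reading is weaker still.

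A second reply is that chance cannot carry the study past 80%, and that a guessing floor common to both techniques shrinks their difference without reversing it. Both statements are right under the model above. They limit the point to what the accuracy figure means.

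Several stronger readings are tempting but unsupported:

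- **That 17.1 credits lucky guesses.** It does not mention guesses or indeterminate calls.
- **That sensitivity, specificity and accuracy must coincide.** This holds only for pooled per-lung tables with complementary calls. In a patient-level left/right table the correct rates for the two sides can differ.
- **That lungs would be counted as 160 independent units.** Section 12.2 sizes by patients, and no text makes the lung the unit.
- **That the cited study's 84%-89% can be converted to detection rates.** Its response format is not given.
- **That the plan suffers a calculable power loss.** Assumed detection of 70% against 50%, independent errors and alpha 0.05 give exact McNemar power of about 27% with forced calls and 68% with detection scoring. The rates are hypothetical, the documents give no auscultation accuracy, and the two figures concern different estimands.

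**Conclusion.** The point holds in this form: with blinding limited to side and entry after bronchoscopic confirmation, a correct call shows at most that the isolated side was identified. As written, the plan would attach the conclusion of 2.2 and 3.2 to data that do not support it.

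Its size depends on the undefined answer. With a left/right call the guessing level is 50%, so 80% and 85% correspond to 60% and 70% detection, and differences between techniques are halved. With a yes/no call, the always-yes score is 100%. The first set of figures assumes the detect-or-guess model; the second assumes that every examined patient is bronchoscopy-confirmed. Both assume examiners draw the inference that the sequence and training make available.

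A reader might go further and conclude that guessing could meet the benchmark or that 80 patients is the wrong number. The calculations above support neither on this ground. The inability to estimate recognition of failed isolation comes from having no planned non-isolated patients, which is a separate limitation that a better response form would not cure.

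**What to change.** **In 6.3**, have each examiner independently record each lung as 'ventilated', 'not ventilated' or 'cannot tell', with both or neither ventilated allowed as a combination. Complete the record before any other result is disclosed.

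**In 17.1**, keep the patient as the unit. Count a patient as correct only if both lungs are called correctly, count 'cannot tell' as not correct, and report how often it occurs.

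**Chance correction.** Report 2 × accuracy − 1 only if a forced left/right call is kept. It must not be combined with 'cannot tell' scoring: an examiner who detects 70% and declines the other 30% scores 70%, and the formula would give 2 × 0.70 − 1 = 40%, penalising the same non-detections twice.

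**In 2.2 and 17.1**, word the conclusion as identifying the isolated side and not as verifying isolation. The narrower wording is needed even with the new form, because the form neither removes the examiners' prior knowledge nor adds non-isolated patients.

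The cost is a few tick-boxes and some sentences, with no extra patients, staff or procedures. The form should be settled before enrolment, since guesses cannot be separated from detections afterwards. The downside is that the reported accuracy may be lower and the claim narrower.

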8.0 Sharing of Results with Subjects*

8.1 Results will not be shared

9.0 Study Timelines*

- An individual study subject's participation in the study should last approximately 15-30 minutes total.
- All study subjects should be enrolled within 1 year of study start.
- The study should be completed within 2 years of study start.

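### With inspiratory time fixed at 1 second for ages 0-21, section 6.1 offers no way to reach normocapnia without an inverse I:E ratio once more than 240 ml/kg/min is needed

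*Combined protocol and SAP*

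**What the plan says.** Section 6.1 imposes study ventilator settings: "The ventilator settings will be standardized until all of the study measurements and data have been collected". Three of them interact: "RR titrated to achieve normocapnia", "Inspiratory time 1 second" and "TV set at 6-8 ml/kg". Tidal volume scales with weight and rate is adjusted to the patient, but inspiratory time is one absolute value. No maximum rate, I:E limit, or age- or weight-based alternative is given.

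Section 10.2 admits ages 0 to 21 and lists no exclusions.

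Two sentences bear on flexibility. In 6.1, the primary anesthesiologist has this role: "They will decide prior to and during the case whether the patient is appropriate for and able to complete the study protocol". At the end of 6.3, after the examinations and the start of surgery have been described: "The intraoperative ventilation strategy will be at the discretion of the attending anesthesiologist".

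Section 6.2 provides the record: "After anesthetic induction the following ventilatory parameters will be recorded: tidal volume, peak inflating pressure, inspiratory time, respiratory rate", with a second recording once the lung is isolated. On duration, section 9.0 says "participation in the study should last approximately 15-30 minutes total".

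**The concern.** A fixed inspiratory time and a freely rising rate compete for the same breath cycle. As the rate goes up, all of the shortening comes out of expiration. With tidal volume confined to a narrow band, rate is the main means of controlling carbon dioxide, so a patient with a high ventilatory requirement per kilogram could be pushed to a rate that 1 second of inspiration does not suit.

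The patients most likely to be in that position are the youngest, and age 0 is eligible. If it happens, the anesthesiologist has no option within the protocol to shorten inspiration before the examinations end. What is at stake is the suitability of a study-imposed setting for a few small patients over a short period, and how departures from it are classified.

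**Working it through.** The plan states no figure on this point, so there is none to reproduce. The check is arithmetic on the breath cycle.

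**Inputs (all from 6.1).** Inspiratory time Ti = 1 s. Tidal volume 6 to 8 ml/kg. Rate RR is free, with no ceiling.

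**Formulas.** Cycle length = 60/RR. Expiratory time Te = 60/RR - 1. I:E = 1/Te. Minute ventilation = (6 to 8) x RR.

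| RR (/min) | Cycle (s) | Te (s) | I:E | Minute ventilation (ml/kg/min) |
|---|---|---|---|---|
| 20 | 3.00 | 2.00 | 1:2 | 120-160 |
| 30 | 2.00 | 1.00 | 1:1 | 180-240 |
| 35 | 1.71 | 0.71 | 1.4:1 | 210-280 |
| 40 | 1.50 | 0.50 | 2:1 | 240-320 |
| 45 | 1.33 | 0.33 | 3:1 | 270-360 |
| 50 | 1.20 | 0.20 | 5:1 | 300-400 |
| 60 | 1.00 | 0 | none possible | 360-480 |

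**Rate threshold.** Inspiration exceeds expiration when 60/RR - 1 < 1, that is, when RR > 30/min.

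**Minute-ventilation threshold.** Rate is not imposed alone; it is chosen together with tidal volume. A patient at 40/min on 6 ml/kg receives 40 x 6 = 240 ml/kg/min. The same 240 is delivered at 30/min on 8 ml/kg (30 x 8 = 240), with I:E 1:1 and inside the stated settings. So:

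- up to 180 ml/kg/min (30 x 6), no inversion is needed anywhere in the tidal-volume range;
- from 180 to 240, inversion is avoidable by raising tidal volume towards 8 ml/kg;
- above 240, no permitted combination avoids it. At 8 ml/kg, 320 ml/kg/min needs 40/min (2:1), and 400 needs 50/min (5:1).

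This treats minute ventilation as the measure of carbon dioxide clearance, which is a simplification.

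**Is there an exception elsewhere?** The discretion in 6.3 concerns ventilation during surgery and follows the examinations; 6.1 governs the period before. The primary anesthesiologist's role in 6.1 is to decide whether the patient goes on in the study, and it does not extend to choosing a different inspiratory time. Section 14.0 on withdrawal reads N/A. No exception was found.

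**The case against.** The strongest reply is that the difficulty may never arise. The documents give no expected rates, and without a patient who needs more than 240 ml/kg/min only an identity remains. That stands: the number affected is unknown and could be zero. The view that the youngest are likeliest to be affected is also a clinical expectation that the documents do not state.

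A second reply is that the primary anesthesiologist is responsible for care and can stop a patient at any time, so nobody need be kept on an unsuitable setting. This largely answers the safety worry. It does not repair the rule, because it removes the patient where a small adjustment would do.

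A third is that the documents set no I:E limit, so calling a short spell of inverse ratio undesirable is a clinical preference. That is fair, and it is one reason to rate the point low.

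A reader might infer more than the text supports:

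- *That any rate above 30/min forces inversion on the patient.* It does not. Rates of 31-40/min at 6 ml/kg can be brought to 30/min or below within the tidal-volume range.
- *That patients will be left with no expiratory time.* That needs 60/min, or 360-480 ml/kg/min, and nothing in the documents suggests that any patient requires it.
- *That the accuracy estimate is biased or the youngest patients' data are lost.* No mechanism or size is given for an accuracy effect. A shortened inspiratory time would be visible in the 6.2 record, and the data need not be discarded.

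**Conclusion.** The point holds as a minor gap in a stated rule. Section 6.1 combines an unscaled 1-second inspiration with an uncapped rate and provides no exception. Up to 240 ml/kg/min the settings can be met without an inverse ratio. Beyond that, the choice is inverse-ratio ventilation, abandoning normocapnia, a deviation, or a stop.

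The thresholds follow exactly from the protocol's own settings. Whether any enrolled patient crosses them is an assumption. The exposure is short, and neither the sample size nor the primary comparison is affected. The case for acting is that the correction is cheap and does nothing where it is not needed.

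**What to change.** In 6.1, replace the fixed value with: 1 second, or no longer than 30/RR seconds when RR exceeds 30/min (shorter at the anesthesiologist's discretion). The 1:1 limit is used only because it is where the ratio inverts.

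**Effect.** Nothing changes at or below 30/min. Above it, the longest permitted Ti is 30/RR, and Te is at least as long:

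| RR (/min) | Longest Ti (s) | Te now (s) | Te after, at longest Ti (s) | Mean inspiratory flow after, (6 to 8)/Ti (ml/kg/s) |
|---|---|---|---|---|
| 40 | 0.75 | 0.50 | 0.75 | 8-10.7 |
| 50 | 0.60 | 0.20 | 0.60 | 10-13.3 |
| 60 | 0.50 | 0 | 0.50 | 12-16 |

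**Cost.** One line and IRB review of the amendment. Inspiratory time is no longer identical across patients above 30/min. The same volume is delivered faster, against 6-8 ml/kg/s at present, so peak pressure may rise somewhat, and more so if a still shorter time is chosen. No new data field is needed, since 6.2 already captures inspiratory time, rate and peak inflating pressure.

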12.0 Local Number of Subjects

12.1 80

12.2 Power calculation for this study was based on a previous study reporting the accuracy of ultrasonography (compared to FOB) for confirming lung isolation when using DLTs.¹¹ This study found the accuracy to be 84%-89% depending on which lung was isolated. Assuming that ultrasonography has an overall accuracy of 85%, a two-tailed, one-sample test of proportions would have >80% power to detect a difference of at least 10% when 80 patients are enrolled.

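### The blinded examinations start only after FOB confirms placement, so they contain no FOB-negative patients, and section 17.1 leaves the unit and target condition of its accuracy measures open

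*Combined protocol and SAP*

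**What the plan says.** All references are to the combined protocol and SAP.

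- **Sequence.** Section 6.2 has the device placed, then a clinical check: "Clinical confirmation of effective lung separation will include auscultation with documentation of absence of breath sounds on the operative side". FOB follows. Section 6.3 opens with "Once SLV device placement is confirmed by bronchoscopy"; the drape goes on and only then do the two blinded examiners come in. No section describes a blinded examination of a patient whose placement FOB has not confirmed.
- **Blinding and completion.** Section 6.1 states: "Both the auscultator and ultrasonographer will be blinded to the lung that is isolated". Of the primary anesthesiologist it says: "They will decide prior to and during the case whether the patient is appropriate for and able to complete the study protocol".
- **Analysis.** Section 17.1 compares the "accuracy, sensitivity, and specificity of ultrasonography and auscultation (using FOB confirmation of one-lung isolation as the reference standard") using paired tests of proportions. It does not say whether the unit is the patient or the lung, or which condition counts as positive.
- **Target and planning value.** Section 2.2 expects that "ultrasonography will have at least 80% accuracy for verifying lung separation during SLV as confirmed by FOB", and that ultrasound will be more accurate than auscultation. Section 12.2 says of its source: "This study found the accuracy to be 84%-89% depending on which lung was isolated". It then plans 80 patients on an overall accuracy of 85%, with no unit given.
- **Purpose and signs.** Section 3.2 aims at showing effective isolation without bronchoscopy. Section 3.1 lists the ultrasound signs of a non-ventilated lung, and the endpoint in section 4.1 covers movement or its absence on both sides.

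**The concern.** Sensitivity and specificity against a reference standard need patients, or lungs, on both sides of that standard. The sequence in section 6.3 keeps out every patient whom FOB would classify as not correctly placed. If such a device is repositioned until FOB confirms it, the patient enters as FOB-positive; if not, the patient is never examined by the blinded readers.

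Two things are at stake. First, an examination that is to stand in for FOB must pick up the failures that FOB picks up, and the blinded data hold none. Second, the open unit decides what section 17.1 can report at all and what reaching 80% accuracy would mean. If the choice is left until the data are in, the same readings could be scored in more than one way.

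**Working it through.** **Inputs.** N = 80, planning accuracy 85% and a 10-point difference (12.2); target 80% (2.2); order of procedures (6.2, 6.3); reference standard and measures (17.1). All denominators below are maxima, because section 6.1 allows a patient not to complete the protocol.

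**The plan's own figure.** Section 12.2 states more than 80% power. For a one-sample test of proportions, power = Φ((|p1 − p0| − 1.96·√(p0(1 − p0)/n)) / √(p1(1 − p1)/n)), with two-sided alpha 0.05 assumed because none is stated. With p0 = 0.85, p1 = 0.95, n = 80: (0.1 − 1.96 × 0.0399)/0.0244 = 0.89, so power is 81.4%. Null 0.95 against true 0.85 gives 90.5%. The figure reproduces on those readings, but not for null 0.75 against true 0.85 (55.1%). None of these calculations involves the number of FOB-negative patients, so the power statement does not bear on the gap.

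**Step 1: reference-negative patients.** All examined patients are FOB-confirmed: up to 80 positive, 0 negative.

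**Step 2: what section 17.1 yields under each reading.**

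*Per patient, isolated yes/no.* With 'isolated' as positive, specificity is 0/0; with 'failed' as positive, sensitivity is 0/0. A constant answer of 'isolated' scores 80/80. The exact lower limit is 0.025^(1/80) = 95.5%, so the interval is 95.5% to 100%. If only 60 patients were examined (assumed), 0.025^(1/60) = 94.0%.

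*Per lung.* There are up to 80 isolated and 80 ventilated lungs, so both measures have denominators. If 85% held for either one (assumed; 12.2 gives it as overall accuracy), 68/80 has an exact 95% CI of 75.3% to 92.0%.

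*Per patient, which side is isolated.* Take right-isolated as positive and assume a 40/40 split. With 32/40 right and 36/40 left correct, sensitivity is 80%, specificity 90% and accuracy 68/80 = 85%. A constant answer of 'right' scores 40/80 = 50%, the share isolated on that side.

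*Side naming scored per lung.* If c patients are named correctly, both lungs are right in those c and both wrong in the rest. Sensitivity = c/80, specificity = c/80, accuracy = 2c/160 = c/80. The three coincide here, but not in the per-patient scoring just above.

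**Step 3: effect of the unit on the target.** Suppose 85% is per lung (assumed). Then 136/160 lungs are correct, with 24 errors. If every error falls in a different patient, 80 − 24 = 56 patients have both sides correct (70%). If errors pair within patients, 80 − 12 = 68 do (85%). If errors on the two sides are independent (assumed), the expected share is 0.85² = 72.25%. Accuracy defined as both sides correct could therefore fall below 80% with the planning value met.

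**Step 4: what counts as positive.** Sections 3.1 and 4.1 together give most of an ultrasound definition: no sliding, no B-lines and possibly a lung pulse on a non-ventilated lung, and movement on the other. No rule covers discordant signs. Section 6.3 gives the blinded auscultator no criterion; the one in section 6.2 belongs to the earlier clinical check.

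**The case against.** The best defence is that the empty denominator arises only under the isolated yes/no reading, which the documents support least. Blinding to side has little purpose if the answer carries no side, section 4.1 looks at both lung fields, and section 12.2 describes accuracy by isolated lung. Under a per-lung or which-side reading, sensitivity and specificity exist and a constant answer earns no credit beyond its share. This stands. A reader might infer that the planned measures cannot be estimated at all, or that the primary objective is unanswerable; the documents do not support either inference. Nor do the three measures always collapse into one under side naming, as Step 2 shows.

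It can also be said that the ventilated lung is an indirect control: an operative lung still being ventilated should show the same movement. That is fair for gross failure. It does not extend to partial leak or malposition, and it is not an observation of failed isolation.

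The earlier auscultation in section 6.2 does not fill the gap. It has no stated blinding and no ultrasound counterpart, and section 17.1 does not name it. The surgeon's record of unsuccessful separation is collected, but FOB is the declared reference, so a failure despite confirmed placement is scored as isolated.

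Finally, it would be too strong to say that a positive ultrasound result is undefined, or that sections 12.2 and 2.2 have been shown to use different units. The first is partly defined. The second depends on a source that the documents do not reproduce, so the 70% to 85% range is a conditional bound.

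**Conclusion.** The concern holds and should be fixed. Under the written sequence the blinded examinations include 0 FOB-negative patients, so detection of FOB-detected failed isolation cannot be estimated from them on any choice of unit, and the claim in section 3.2 goes further than the data can. That conclusion rests only on the order of procedures and on the absence of any route for unconfirmed placements.

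The rest depends on the reading. On isolated yes/no, one measure has no denominator and an uninformative answer reaches up to 80/80 (95.5% to 100%). On the per-lung or which-side readings, both measures can be estimated, with a 95% interval of about 75% to 92% for a per-lung measure at an assumed 68/80, and they measure recognition of the ventilated and non-ventilated lung. The effect on the 80% target is conditional on 85% being a per-lung figure. What is wrong is that section 17.1 does not choose among these readings, and that no reading delivers what section 3.2 promises.

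**What to change.** 1. **Section 6.3:** have each blinded examiner record left and right chest separately as ventilated or not ventilated, with 'both' and 'neither' allowed. State how discordant ultrasound signs are resolved and what criterion the blinded auscultator uses.
2. **Section 17.1:** define sensitivity on the isolated side and specificity on the ventilated side. Each uses one lung per patient, so the planned paired tests (McNemar) apply. Use patient-clustered methods for any analysis pooling both lungs.
3. **Sections 2.2 and 12.2:** before data are seen, fix which accuracy (both sides correct, or per lung) is tested against 80%, and confirm that 12.2 assumes the same one. If it does not, redo 12.2 for the chosen measure.
4. **Reporting:** give the number of placements that FOB did not confirm and that were therefore not examined. Limit the conclusion to identifying the ventilated and non-ventilated lung after FOB-confirmed placement, and state that detection of FOB-detected failed isolation is not estimated.
5. **Optional:** a descriptive tabulation against the surgeon's recorded separation result, noting that the patient is repositioned in between. There may be few failures.

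The cost is one more line on the data form, some rewording, possibly a revised 12.2, and a narrower claim than section 3.2. Care and the order of procedures are unchanged. The missing FOB-negative patients stay missing: the change makes that explicit but does not cure it.
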